1.12 STUDY DURATION

The study will be conducted over a maximum of nine (9) dialysis sessions (first three (3) are controls) for each patient. Typically, a patient will have three sessions in one week so that the study will last three (3) weeks per patient. Each session usually lasts around three hours. Any adverse events that are reported after the study session (e.g., a hematoma in the days following the session) will also be catalogued and reported. Adverse events will be recorded up until the next dialysis treatment or for one week following the last session if no additional sessions are planned.

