5.1 Overall Design

This study is a prospective, multi-center, single-arm study with subjects acting as their own control designed to confirm the safety, performance, and usability of the V Needle, a new safety needle for use during in-clinic hemodialysis that is designed to automatically generate a partial occlusion of the internal fluid path and trigger the hemodialysis machine to alarm and shut off if a complete dislodgement of the venous needle from the arm inadvertently occurs.

For the first three (3) control sessions, consenting subjects will undergo usual hemodialysis sessions with a commercially available device. For the remaining six (6) test sessions, subjects will be cannulated with a V Needle in place of a usual venous line AV fistula set.

The hemodialysis sessions will be conducted in the clinic. Subjects will be observed by a clinician for the duration of each session. Clinicians will monitor the session for any abnormal disruptions, therapy interruptions, and/or adverse events, including hemolysis, due to V Needle presence. All machine blood alarms, therapy interruptions, and/or partial or complete needle dislodgements will be recorded and immediately corrected. Clinicians will be responsible for identifying adverse events as they occur and will activate established facility emergency response plans if necessary. A clinician will perform cannulation.

Cannulation site and surrounding tissue will be examined by the nurse and assessed for any locally induced trauma before and after treatment.

A survey will be completed by the users to assess usability of the V Needle.

After the first five (5) patients will be enrolled, and data through the last visit of the fifth patient is available, this data will be submitted to the FDA while study enrollment and visits continue. No Hemotek Medical V Needle treatments will occur until after FDA has reviewed the data from the first 5 patients and allows the study to proceed. Data will also be submitted to the FDA after the tenth patient completes their last visit and data is available. After the tenth patient, study enrollment and visits can continue, but no Hemotek Medical V Needle treatments will occur on the final 5-10 patients until the FDA allows the study to proceed. After FDA has found the data for the first 10 patients acceptable, the rest of the study can continue until the end.

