5.3 End of Study Definition

A participant is considered to have completed the study if they have completed all follow-up visits. It is expected that 15 subjects will undergo 9 treatments each. In the event that some of these patients do not complete the full set of treatments, additional subjects (up to 20 total) will be recruited until 87 V Needle treatments are completed and all patients have completed their study visits.

After the first five (5) patients will be enrolled, and data through the last visit of the fifth patient is available, this data will be submitted to the FDA while study enrollment and visits continue. No Hemotek Medical V Needle treatments will occur until after FDA has reviewed the data from the first 5 patients and allows the study to proceed. Data will also be submitted to the FDA after the tenth patient completes their last visit and data is available. After the tenth patient, study enrollment and visits can continue, but no Hemotek Medical V Needle treatments will occur on the final 5-10 patients until the FDA allows the study to proceed. After FDA has found the data for the first 10 patients acceptable, the rest of the study can continue until the end.

If there are any deaths or three SADEs during the study device period that require medical or surgical intervention, study enrollment and further visits will be stopped, and an assessment (in conjunction with the DSMB and FDA) will be enacted.

6 Study Population

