9.2.2 AE and Device Deficiency Documentation

All AEs will be monitored for all participants, from the time of signing consent through to the final study visit. All AEs, including SAEs, must be detailed in the source documents and reported in a timely manner to the Sponsor by completing an AE page in the CRF. Each unique event must be documented separately.

AEs can be based upon subject report, questionnaires, medical reports or other medical examinations. AEs should be documented in terms of a medical diagnosis. When this is not possible, the AE should be documented in terms of signs and/or symptoms observed by the Investigator or reported by the subject at each study visit. For each medical diagnosis or sign and/or symptoms the Investigator will provide information on dates (onset/resolution), severity, relationship to the medical device, action(s) taken and outcome.

Any AEs should be followed until the event is resolved (with or without sequelae). If an event is ongoing at the time of study completion or termination, the participant will be followed until resolution or Investigator determination that the subject's condition is stable. Documentation of stabilization must be recorded in the participant's source documents. If the Investigator learns of any SAE at any time after a participant has been discharged from the study, and he/she considers

the event reasonably related to the study device and/or study procedure, the Investigator will record the occurrence in the subject's source documents and promptly notify the Sponsor.

If adverse events occur, the first concern will be the safety of the subject. Appropriate medical intervention will be made as soon as possible. Treatment of any AEs is at the sole discretion of the Investigator and according to current good medical practice. Any medication administered for the treatment of an AE should be recorded in the CRF.

All device deficiencies, including serious incidents (a device deficiency that might have led to a SADE if a) suitable action had not been taken, b) intervention had not been made, c) if circumstances had been less fortunate), shall be documented throughout the study in the source documents and appropriately reported on a device deficiency page of the CRF.

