10.3 Statistical Analyses

10.3.1 Performance Endpoint Analysis

Although not a randomized study, each subject dialysis session will be performed using either the test needle or a control needle. The sites are instructed to perform 3 control sessions first and then 6 test sessions per enrolled subject, and in the case that a site deviates from this order, performance measure will be analyzed based on the needle used. Assuming there will be a 20% rate of attrition/drop-out, the remaining 18 subjects would contribute 108 test and 54 control sessions. Data will be pooled by session type (test vs. control) from all sites (no by-site analyses are planned).

The primary performance analysis will test the non-inferiority hypothesis as a difference of proportions between the test and control groups using a one-sided Farrington-Manning Score Test at a significance level of $\alpha=0.025$.

Additionally, the primary performance measure will be analyzed on the subject-level (utilizing a non-inferiority margin of 0.05) by testing the difference in mean success rates per subject across treatment groups using a one-sided paired t-test at a significance level of $\alpha=0.025$.

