10.3.2 Safety Endpoint Analysis

The incidence rates of adverse events (including those listed under the primary and secondary safety endpoints) will be calculated as the number of events per number of treatments as well as tallied per subject. Adverse event rates will be summarized with 95% exact binomial confidence bounds for both the investigational and control groups.

The adverse events of each group will also all be stratified by their (1) seriousness, (2) severity, (3) relatedness to device, (4) relatedness to procedure, and (5) anticipated status.

Any events with onsets occurring between sessions will be associated with the group representing the device used at the last session.

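### The rule for between-session adverse events makes the V Needle versus control AE comparison depend on FDA hold length and on follow-up after Visit 9

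*Combined protocol and SAP*

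**What the plan says.** **Attribution and rate (10.3.2).** "Any events with onsets occurring between sessions will be associated with the group representing the device used at the last session". Incidence rates "will be calculated as the number of events per number of treatments as well as tallied per subject".

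**What counts as a treatment.** Section 5.3 uses the word for the study sessions: "It is expected that 15 subjects will undergo 9 treatments each". Section 10.3.1 plans the denominators: "the remaining 18 subjects would contribute 108 test and 54 control sessions". Table 1 in 1.23 provides a Therapy Assessment Form for Visits 1-9 only, so routine dialysis outside those visits is neither recorded nor counted.

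**AE collection.** Section 9.2.2: "All AEs will be monitored for all participants, from the time of signing consent through to the final study visit". Section 9.2.13 runs from consent to 7 days after the last day of participation and has the investigator ask at each visit about events since the previous one. Section 1.12 differs: "Adverse events will be recorded up until the next dialysis treatment", or for one week after the last session if no more are planned.

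**The holds (5.1).** After the first five patients, "this data will be submitted to the FDA while study enrollment and visits continue", with V Needle use suspended. After the tenth, "no Hemotek Medical V Needle treatments will occur on the final 5-10 patients until the FDA allows the study to proceed". A later subject can therefore complete control Visits 1-3 and then wait for Visit 4.

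**After Visit 9 (9.1.4).** The final contact is 7-10 days later, by phone or at a usual dialysis session.

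**The concern.** The numerator and denominator cover different periods. While a subject waits between Visits 3 and 4, dialysis continues on a commercial needle. Events in that wait go to control, but the sessions that accompany them are not counted. The same happens on the other side after Visit 9: events go to the V Needle although any routine dialysis by then is off-study and uncounted. Events before Visit 1 have no preceding study session, so the rule gives them no home.

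Comparing AE rates with the subject's own control sessions is a stated purpose of the trial (1.1, 1.8, 5.2, 7.3). Under the rule as written, two needles with identical risk can show different rates, and which one looks worse depends on how long FDA review takes. The control denominator is half the test denominator, so each misplaced event moves the control rate twice as far.

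**Working it through.** **Plan's own figures.** 18 subjects × 6 = 108 test sessions and 18 × 3 = 54 control sessions, as in 10.3.1.

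**Inputs from the documents.** Three sessions a week (1.12); 3 control then 6 test sessions (5.1); final contact 7-10 days after Visit 9 (9.1.4); visit sequence within 40 days of baseline (1.24).

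**Assumptions.** A constant daily AE hazard, equal for both needles; a Monday/Wednesday/Friday schedule with Visit 1 on Monday; continuous collection to the final visit; session in 10.3.2 read as study session, so events after Visit 9 go to the needle used at Visit 9. The number of subjects held (k) and days held (g) are not in the documents and are varied.

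**Calendar.** Visits 1-9 fall on days 0, 2, 4, 7, 9, 11, 14, 16, 18. Visit 1 to Visit 4 is 7 days; Visit 4 to Visit 9 is 11 days.

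**Formulas, AE-days credited per counted session (N = 18).**
- Control = (7N + k·g) / (3N) = (126 + k·g) / 54
- Test = (11 + tail) / 6, which is 18/6 = 3.0 for a 7-day tail and 21/6 = 3.5 for a 10-day tail

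| Subjects held × days | Control | Control/test, 7-day tail | Control/test, 10-day tail |
|---|---|---|---|
| none | 126/54 = 2.33 | 0.78 | 0.67 |
| 5 × 7 | 161/54 = 2.98 | 0.99 | 0.85 |
| 5 × 14 | 196/54 = 3.63 | 1.21 | 1.04 |
| 10 × 11.7 (5 routine sessions × 7/3 days) | 242.7/54 = 4.49 | 1.50 | 1.28 |
| 13 × 14 | 308/54 = 5.70 | 1.90 | 1.63 |
| 13 × 21 | 399/54 = 7.39 | 2.46 | 2.11 |

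The 13 held subjects are all those after the first five (18 − 5).

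**Break-even.** The groups balance when 7 + average hold = 3 × (11 + tail)/6. The right side is 9 or 10.5, so the average hold is 2.0 or 3.5 days per subject (36 or 63 subject-days in all).

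**Longest hold.** With day 0 as baseline, Visit 9 by day 40 allows 40 − 18 = 22 days, about 9 routine sessions against 3 counted. If the final contact must also fall within 40 days, the limit is 22 − 10 = 12 to 22 − 7 = 15 days, so the 21-day row is an upper case.

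**Longer tail.** With the extra 7 days in 9.2.13, the tail is up to 17 days and the test figure is 28/6 = 4.67. The ratio is then 2.33/4.67 = 0.50 with no hold and 7.39/4.67 = 1.58 for 13 × 21.

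**Window closed at the next dialysis session of any kind.** Control is 7/3 = 2.33. Test runs from day 7 to the session after Visit 9. On this calendar that is day 21, giving 14/6 = 2.33 and a ratio of 1.00. If that session comes two days after Visit 9, test is 13/6 = 2.17 and the ratio 1.08. Neither depends on hold length.

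**The case against.** The case against acting has real content. No document gives FDA review times or says how many subjects will wait. Continued visits are allowed, not required, and 1.24 expects sequential sessions within 40 days, so sites have reason not to start control visits long before release. If 1.12 governs, recording stops at the first routine session in a hold and that side of the problem largely disappears. The AE comparison is descriptive, with no hypothesis test in 10.3.2, and onset dates are collected, so events could be re-sorted later. The primary safety measure is little touched: 9.2.1 defines device effects for the investigational device only.

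These points limit the size and the consequence. They do not remove the defect. Sections 9.2.2 and 9.2.13 contradict 1.12. The per-subject tally uses the same attribution and makes no allowance for time at risk. Splitting by relatedness does not repair a comparison of all AEs or SAEs. Re-sorting after the data are seen is weaker than a rule set beforehand.

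A reader might go further and infer that the control rate is always inflated in the V Needle's favour, or that events between consent and Visit 1 also fall to control. The documents do not support either. Counting only the control side for 10 subjects held for 5 routine sessions gives (8 × 3 + 10 × 8)/54 = 1.93, but the same rule credits the period after Visit 9 to the V Needle, which brings the net ratio to 1.3-1.5. With no hold, the ratio is below 1. Events before Visit 1 reach control only if session includes routine dialysis, whereas 10.3.1 uses the word for the study's control and test sessions. On that usage they are simply unassigned.

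**Conclusion.** The point holds as a distortion whose direction is not fixed. Under 10.3.2, hold-gap events inflate the control AE rate, post-Visit 9 events inflate the V Needle rate, and pre-Visit 1 events have no assignment. For needles of equal risk, the comparison leans against the V Needle with no hold or very short holds. It leans in its favour once the average hold exceeds about 2.0-3.5 days per subject, and the lean is material for holds of about two weeks in most later subjects. These figures rest on the constant hazard, the regular schedule, the study-session reading of the rule and the assumed hold patterns. The analysis exposed is the descriptive AE/SAE comparison with control. The change should be made because it is cheap and the comparison is a stated purpose of the trial.

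**What to change.** 1. Reconcile 1.12 with 9.2.2 and 9.2.13 on the AE recording period. Continuous recording can stay; the change needed is to attribution.
2. In 10.3.2, credit an AE to a needle for the comparative rate only if onset falls from the start of a study session on that needle to the start of the next dialysis session of any kind. The denominator is the number of study sessions on that needle. Define session and treatment accordingly.
3. Report events before Visit 1, in a hold gap after the first routine session, and after the first dialysis session following Visit 9 in a separate column outside both comparative rates, so that none is lost.
4. Count any event judged related to the V Needle in the ADE and SADE rates whatever its onset.

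Cost: SAP wording and the date of the next dialysis session on the CRF. The small downside is that fewer events enter the comparative rates.

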10.3.3 Usability and Additional Measures

The results from the clinician and patient surveys (formatted on ordinal scaling) will each be summarized using the 5-point Likert scoring system (e.g., 5=strongly agree, 4=agree, 3=neither agree or disagree, 2=disagree, 1=strongly disagree) to represent user responses on a symmetric range, with overall item scores to represent usability measures. The usability of the V Needle will be assessed from the clinician and patient survey scores submitted for the needle device used at the end of each session. This will be done using a Mann-Whitney-Wilcoxon (MWW) test, which will assess differences in mean ranks of clinician/patient survey scores given to the V Needle and control devices, as applicable.

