1.1 PROTOCOL SUMMARY

In patients undergoing hemodialysis for the treatment of end-stage renal disease, Venous Needle Dislodgement (VND) is a rare, but potentially fatal situation in which the needle delivering a patient's blood back to the body after filtration by a dialysis machine becomes inadvertently disconnected from the patient. Hemotek Medical Inc. has developed the V Needle, a venous needle return that is designed to reduce patient risk from exsanguination-related injury or death. This clinical study will serve as a confirmatory study to gain FDA marketing clearance of the Hemotek V Needle system in the clinical setting. During this study, we will determine the ability of the V Needle to successfully deliver appropriate hemodialysis therapy per the facility's guidelines. It will also be used to determine if the V Needle triggers false blood alarms under normal operating conditions. This study will also be used to demonstrate the V Needle meets effective usability criteria. Rates of adverse events and ability to complete the hemodialysis session will be compared to the rates recorded using commercially available devices during the hemodialysis sessions prior to the use of the Hemotek V Needle.

This study is a prospective, multi-center, single-arm study with subjects acting as their own control designed to confirm the safety, performance, and usability of the V Needle, a new safety needle for use during in-clinic hemodialysis that is designed to automatically generate a partial occlusion of the internal fluid path and trigger the hemodialysis machine to alarm and shut off if a complete dislodgement of the venous needle from the arm inadvertently occurs.

The study is an open-label, non-randomized, single arm, multi-center trial with subject's serving as their own control. For the first three (3) control sessions, subjects will undergo usual hemodialysis sessions with a commercially available device. For the remaining six (6) sessions, subjects will be cannulated with a V Needle in place of a usual venous line AV fistula set.

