1.4 STUDY OBJECTIVES

The study is designed to confirm the safety, performance, and usability of the Hemotek V Needle A.V. Fistula Set for temporary cannulation for hemodialysis in the treatment of end-stage renal disease patients in the clinical setting.

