10.1 Statistical Hypotheses

10.1.1 Sample Size

The sample size was determined to compare the rate of successful treatments between hemodialysis sessions with the test needle compared to the control needle.

The hypothesis test for the primary performance measure is defined as follows:

$$H_0: p_T - p_C \leq -\delta$$

$$H_1: p_T - p_C > -\delta$$

where p_T is the probability of a successful hemodialysis treatment session with the V Needle (test), p_C is the probability of a successful hemodialysis treatment session with a commercially available device (control), and δ is the non-inferiority margin.

This sample size estimation is based on the following assumptions:

- The expected success rate for both devices is 98%
- The expected difference between the test and control treatment groups is 0%
- There is a test-to-control sampling ratio of 2:1
- A non-inferiority margin of 8% ($\delta = 0.08$)
- Use of a one-sided Farrington-Manning Score Test with 85% power and at a one-sided 2.5% significance level

Based on these assumptions, a statistically powered sample size of 87 test (V Needle) sessions is required for the primary endpoint^{4,5}.

The total sample size is therefore determined to be 108 test sessions with 18 subjects required to account for 20% attrition and/or any of the 6 V Needle sessions being missed.

The primary performance analysis will test the non-inferiority hypothesis as a difference of proportions between the test and control groups using a one-sided Farrington-Manning Score Test at a significance level of $\alpha=0.025$.

Additionally, the primary performance measure will be analyzed on the subject-level (utilizing a non-inferiority margin of 0.05) by testing the difference in mean success rates per subject across treatment groups using a one-sided paired t-test at a significance level of $\alpha=0.025$.

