10.4 Other Statistical Considerations

10.4.1 General/Summary Metrics

Simple descriptive statistics will be displayed for all relevant variables collected under the study, and be presented on the session-level (between-subject), with the exception of the additional analysis of the primary performance measure which will be done on the individual-level (within-subject).

Continuous variables will display number of observations/counts measured, mean, standard deviation, median, min/max, Q1/Q3, and 95% confidence intervals where appropriate; categorical variables will display frequency counts and percentages.

These variables will include but are not limited to the following:

- Subject demographics (including age, gender, weight, height, etc.)
- Medical history characteristics (including concomitant medication, duration in which subject was diagnosed with renal disease, any concurrent ailments, etc.)

Unless otherwise specified, all p-values will be considered significant at $\alpha=0.05$ if tests are two-sided and $\alpha=0.025$ if tests are one-sided.

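### Usability is to be demonstrated and confirmed, but no criterion is stated and the only inferential test is a difference test, which cannot show it

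*Combined protocol and SAP*

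**What the plan says.** The claim is confirmatory. Section 1.1, repeated in 3.1, states: "This study will also be used to demonstrate the V Needle meets effective usability criteria". Section 1.4, repeated in section 4, states: "The study is designed to confirm the safety, performance, and usability of the Hemotek V Needle A.V. Fistula Set".

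The analysis is in 10.3.3. Survey results "will each be summarized using the 5-point Likert scoring system", with overall item scores standing for usability. Usability is then assessed from the end-of-session scores: "This will be done using a Mann-Whitney-Wilcoxon (MWW) test, which will assess differences in mean ranks of clinician/patient survey scores" for the V Needle and control devices, where applicable. Section 10.4.1 adds general descriptive statistics and the default significance level: "all p-values will be considered significant at $\alpha=0.05$ if tests are two-sided and $\alpha=0.025$ if tests are one-sided". The sidedness of the Mann-Whitney-Wilcoxon test is not stated.

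Sections 1.19, 4.4 and 9.1.3 mark the patient survey and two clinician items (footplate fully depressed, feelings about patient risk) as V Needle only. The Schedule of Activities agrees: it has no patient survey at control sessions. The clinician items scored on both needles are use according to the IFU, ability to cannulate and ability to see flashback.

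The surveys are listed as additional performance measures, and 1.18 says that no secondary performance measure is powered.

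**The concern.** A study that says criteria will be met has to state them. Without a target score, a margin, a key item or a decision rule, no survey result could fail, and the interpretation is left until the data are in.

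The difference test does not fill the gap, because its null hypothesis is that the two needles score alike. Failure to reject becomes more likely as surveys become fewer or noisier, so it is not evidence of comparability. Rejection in the wrong direction would show that the V Needle scores worse. For V Needle-only items the test cannot be run at all.

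At stake is one of the three stated objectives of a study meant to support marketing clearance (1.5). A real loss in ease of cannulation or flashback visibility could be reported as no significant difference, with nothing in the plan to say how that should be read.

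**Working it through.** **1. Claim against method.** The same protocol handles performance differently:

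| | Performance (10.1.1, 10.1.2) | Usability (10.3.3) |
|---|---|---|
| Margin or threshold | 0.08 | none |
| Hypothesis | one-sided non-inferiority | difference in mean ranks |
| Rule for concluding success | rejection of the null | none |
| V Needle-only items | not applicable | no comparator, no benchmark |

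This comparison carries the point. No power calculation is needed for it: even a large, correctly clustered difference test could not show that unstated criteria are met.

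**2. Session counts.** The documents give no power, effect size or SD for usability, so there is no usability figure to reproduce. The counts come from the primary endpoint: "a statistically powered sample size of 87 test (V Needle) sessions is required for the primary endpoint", and recruitment can end there, since "additional subjects (up to 20 total) will be recruited until 87 V Needle treatments are completed". At the 2:1 ratio, 87 test sessions go with 43 or 44 control sessions. Exact enumeration of the Farrington-Manning test (98% v 98%, margin 0.08, one-sided 0.025) gives 85.3% power at 87/43 and 85.5% at 87/44, so the stated 85% reproduces. The asymptotic formula gives about 115 test sessions, but nothing here turns on that. The planned total is larger: "the remaining 18 subjects would contribute 108 test and 54 control sessions". Fifteen full completers would give 15 × 6 = 90 test and 15 × 3 = 45 control sessions. Twenty would give 120 and 60.

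**3. Illustrative miss rate.** Assumptions that are not in the documents: a true V Needle loss of 0.5 SD, independent sessions, near-normal scores and a two-sided 0.05 test. With the rank test's efficiency of 3/π under normality,

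SE = √[(1/n_T + 1/n_C) × π/3], and miss rate = 1 − Φ(0.5/SE − 1.96).

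| Test/control | SE | 0.5/SE − 1.96 | Power | Missed |
|---|---|---|---|---|
| 87/43 | 0.191 | 0.66 | 74.6% | 25.4% |
| 87/44 | 0.189 | 0.68 | 75.2% | 24.8% |
| 90/45 | 0.187 | 0.72 | 76.3% | 23.7% |
| 108/54 | 0.171 | 0.97 | 83.4% | 16.6% |
| 120/60 | 0.162 | 1.13 | 87.1% | 12.9% |

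Simulation with continuous scores gave 26% at 87/44, 24% at 90/45 and 17% at 108/54.

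**4. Sensitivity.**
- *Five-point scales.* In simulations with a loss of about 0.46 to 0.51 observed SD, 29% to 46% of losses were missed at 87/44 and 21% to 38% at 108/54. Ceiling effects gave the worst results.
- *Repeated sessions.* At 90/45 with an assumed intraclass correlation of 0.1 to 0.3, the miss rate is about 20% to 23% if the correlation is purely within subject and shared by both needles. It is about 37% to 54% if information is instead cut by a design effect of 1 + 3.5 × ICC (an average of 4.5 sessions per subject and needle). Clustering can therefore move the figure either way.

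**The case against.** The strongest reply is that usability was never meant as a tested endpoint. The surveys are additional, unpowered measures, and a miss rate for something never powered does not show a design error. That stands, which is why the miss rate is only illustrative.

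Several stronger readings are tempting, and the documents do not support them:

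- *A non-significant result will be taken as proof.* No section says so. The defect is that no rule is given either way.
- *Usability will be judged on a p-value alone.* Section 10.3.3 also plans Likert summaries, and 10.4.1 plans descriptive statistics, with confidence intervals for continuous variables where appropriate. A reader would see the scores. What is missing is a benchmark to read them against.
- *A serious handling problem would go unseen.* Ability to cannulate, achieved flow and achieved treatment time are recorded separately for both needles. Sessions left incomplete because of a vascular access issue count against the primary endpoint, which has a margin.
- *A margin test would work without extra subjects.* That depends on a margin and an SD that the documents do not give. With an assumed 0.5 SD margin, equal needles and independent sessions, non-inferiority power for a rank-based comparison is about 83% at 108/54 and 75% at 87/44. Repeated sessions could change both figures.

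None of this answers the mismatch between a promise to demonstrate and confirm usability and an analysis that has no criterion.

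**Conclusion.** The concern holds as a mismatch between claim and method. The plan cannot support its own statement that usability criteria are met, because none are stated, its one inferential test addresses a different question, and the V Needle-only items have nothing to be judged against. This conclusion rests on the text and not on any simulation.

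The size is indicative only: about one assumed 0.5 SD loss in six is missed at 108/54, and about one in four at the 87-session minimum. Both figures assume independent sessions and a two-sided 0.05 test, and clustering and ceiling effects can change them. A reader might take one in four as a property of the design, but at the plan's own 108/54 it is about 17%. The primary non-inferiority conclusion is unaffected.

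**What to change.** In 10.3.3:

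1. For clinician items scored on both needles, report the V Needle minus control difference with a 95% confidence interval that respects repeated sessions within subject, for example one based on within-subject differences in mean score.
2. State that a non-significant Mann-Whitney-Wilcoxon p-value will not be read as usability shown.
3. Allow usability to be called demonstrated or confirmed only if a criterion set by the sponsor before data review is met. This means a margin for a named item or overall score on both needles, and a threshold that the lower confidence bound must exceed for V Needle-only items. The documents give no basis for particular values, so the sponsor must justify them and check power, allowing for repeated sessions, once they are chosen.

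If no criterion is set, change *demonstrate* and *confirm* to *describe* for usability in 1.1, 1.4, 3.1 and section 4, and match the same wording in 1.3, 1.8, 5.1 and 5.2.

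The cost is protocol wording and a short analysis of data already collected. The downside is that the usability claim can then fail, or becomes descriptive.
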